### **7.7. Visual Acuity**

Descriptive statistics of the observed and change from baseline Snellen VA expressed as equivalent logMAR will be tabulated for each eye by visit (see definition of baseline in Section 7) and cohort. Only the results from visits during the extension plus the appropriate baseline visit will be presented. A subject data listing will be provided.

### **7.8. Intraocular Pressure**

Descriptive statistics of the observed and change from baseline IOP will be tabulated for each eye by visit and cohort. Only the results from visits during the extension plus the appropriate baseline visit will be presented. A subject data listing will be provided.

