
Methodology: This is an open-label extension of OTX-101-2016-001, a randomized, multicenter, double-masked, vehicle-controlled study in which subjects were randomized to 1 of 2 treatment arms and treated for 12 weeks as follows:
 
 • OTX-101 0.09% (N = ■■■ subjects) • Vehicle (N = ■■■ subjects) 
Subjects successfully completing Study OTX-101-2016-001 may be eligible to enroll in this 40 to 52 week open label extension study in which all subjects will receive OTX-101 0.09% therapy. Subjects may also use unpreserved artificial tears, as needed. Subjects assigned to OTX-101 0.09% in Study OTX-101-2016-001 will participate for 40 weeks. Subjects assigned to vehicle in Study OTX-101-2016-001 are eligible to participate for 52 weeks. Both subject sets will total 52 weeks of participation receiving OTX-101 0.09%.
 
Subjects may enroll in Study OTX-101-2016-002 for up to 14 days following completion of Visit 5 of Study OTX-101-2016-001. At Visit 5a, sites will obtain signed informed consent and dispense study medication. If Visit 5a is not conducted on the same day as Visit 5 of Study OTX-101-2016-001, any female subject of childbearing potential must also have a negative urine pregnancy test. Study “Day” approximately reflects the cumulative number of days of exposure to study drug since the baseline visit of Protocol OTX-101-2016-001, regardless of actual calendar time elapsed.
 
Subjects will self-administer study medication topically to both eyes BID for 40 to 52 weeks depending on their treatment assignment in Study OTX-101-2016-001. Safety evaluations for all subjects will be conducted at study visits on Days 182, 273 and 364; the window for Visits 6 (Day 182) and Visit 7 (Day 273) will be ± 7 days; the window for Visit 8 (Day 364) will be +14 days for those subjects assigned to OTX-101 0.09% in Study OTX-101-2016-001. (± 14 days for subjects assigned to vehicle in Study OTX-101-2016-001, participating for 52 weeks in Study OTX-101-2016-002). Subjects assigned to vehicle in Study OTX-101-2016-001, participating for 52 weeks in Study OTX-101-2016-002, will also be evaluated at Visit 9 (Day 448), which will have a visit window of +14 days. Both eyes will be assessed at each visit. Adverse events and concomitant medications will be documented from signing of informed consent to the subject’s final visit.
	

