7. SELECTION AND WITHDRAWAL OF SUBJECTS

7.1. Subject Inclusion Criteria

The subject will be included if he/she meets the following inclusion criteria:

1. Successful completion of participation in Protocol OTX-101-2016-001.
2. All subjects must provide signed written consent prior to participation in any study related procedures.
3. Female subjects of childbearing potential must have a negative urine pregnancy test at Visit 5 (Day 84) of Protocol OTX-101-2016-001 or at Visit 5a of Protocol OTX-101-2016-002, if conducted at a later date. Women of childbearing potential (i.e., women who are not either postmenopausal for one year or surgically sterile) and men who have partners of childbearing potential must use an acceptable form of contraception throughout the study.
4. Corrected Snellen visual acuity (VA) of better than 20/200 in both eyes at Visit 5 (Day 84) of Protocol OTX-101-2016-001.

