10.1. Visit 5a

Subjects will provide written informed consent and then will be evaluated with respect to the inclusion/exclusion criteria. Assessments conducted at Visit 5 of Study OTX-101-2016-001 are not repeated.

If Visit 5a is not conducted on the same day as Visit 5 of Study OTX-101-2016-001, the following procedures will be conducted.

- AE assessment
- Concomitant medication review
- Urine pregnancy test (women of childbearing potential only)

Subjects who meet all inclusion/exclusion criteria will be assigned a kit of study medication and are again instructed in topical ocular drop administration procedures.

- Dispense study medication

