11.8. Safety Analyses

Safety and tolerability data will be presented in tables of descriptive statistics and frequency distribution. All summary tables will be supported with individual subject data listings. For all subjects enrolled in Study OTX-101-2016-002, the safety data recorded during Study OTX-101-2016-001 will be merged to produce a dataset encompassing one year of exposure to treatment.

AEs that occurred during the run-in period on vehicle of Protocol OTX-101-2016-001 will be summarized separately from AEs that occur from the first dose of double-masked treatment on Day 0 of that protocol to the Day 364 or Day 448 visit of Protocol OTX-101-2016-002.

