### **5.1. Safety Analysis Populations**

The safety population will include all patients who were enrolled in Study OTX-101-2016-002 and received at least one dose of the study medication.

Summaries will be presented by the following groups of subjects:

1. subjects assigned to the OTX-101 0.09% arm in Study OTX-101-2016-001; i.e., those subjects with 12 months exposure to active drug.
2. subjects assigned to the Vehicle arm in Study OTX-101-2016-001; i.e., those subjects with at least 9 months of exposure to active drug.

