### **Definition of Baseline:**

Baseline measurements will be the last measurement for the corresponding variable prior to the first dose of OTX-101 0.09%. For those initially randomized to OTX-101 0.09%, baseline would be the day of randomization (Day 0). For those initially randomized to Vehicle, baseline would be the day of the first dose of OTX-101 0.09% in the extension phase.

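### SAP 7.7 and 7.8 leave out the Study 001 on-drug visits, so the OTX-101-origin cohort has no scheduled on-drug VA result (and probably no IOP result) tabulated before Day 182

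*SAP*

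**What the plan says.** SAP 7.7 (Visual Acuity) and SAP 7.8 (Intraocular Pressure) carry the same display rule: "Only the results from visits during the extension plus the appropriate baseline visit will be presented".

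Which baseline is appropriate depends on the Study 001 arm. Under Definition of Baseline in SAP 7, subjects randomised to OTX-101 0.09% use the day of randomisation in Study 001, Day 0. For the other arm, "For those initially randomized to Vehicle, baseline would be the day of the first dose of OTX-101 0.09% in the extension phase". SAP 5.1 describes the OTX-101-origin cohort as "those subjects with 12 months exposure to active drug".

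On what was measured and when:

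- Protocol 10.1 says of entry to the extension: "Assessments conducted at Visit 5 of Study OTX-101-2016-001 are not repeated". The Schedule of Procedures marks neither VA nor IOP at Visit 5a.
- Protocol 7.1 makes this an entry condition: "Corrected Snellen visual acuity (VA) of better than 20/200 in both eyes at Visit 5 (Day 84) of Protocol OTX-101-2016-001". VA was therefore recorded at Visit 5.
- The protocol synopsis gives the extension examinations: "Safety evaluations for all subjects will be conducted at study visits on Days 182, 273 and 364". Vehicle-origin subjects have a further visit on Day 448.

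On the use of Study 001 data, protocol 11.8 says that, for everyone enrolled in the extension, "the safety data recorded during Study OTX-101-2016-001 will be merged to produce a dataset encompassing one year of exposure to treatment". Protocol 11.5.1.1 adds that certain analyses will use the combined safety data of both protocols for subjects with a full year on active drug. SAP 8 records no changes from the protocol.

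**The concern.** The OTX-101-origin cohort earns its 12-month label by counting the 12 weeks on drug in Study 001, yet the VA and IOP tables show nothing measured on drug in those weeks. Visit 5 falls in Study 001, so the display rule removes it for these subjects. For vehicle-origin subjects the last value before OTX-101 must come from Study 001, normally Visit 5, and it is kept as their baseline.

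At stake is the early part of the one-year safety description, in a study whose only objective is long-term safety. A VA loss or IOP rise that was present at Day 84 and had resolved by Day 182 would not appear in Tables 14.3.4 or 14.3.5 for this cohort. A reader comparing the protocol with the SAP would also not learn that the Study 001 values had been left out, because SAP 8 reports no change.

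**Working it through.** **Inputs.** Visit 5 and Visit 5a are nominal Day 84; Visits 6, 7, 8 and 9 are Days 182, 273, 364 and 448 (Schedule of Procedures; protocol 10). Visit 6 has a window of ±7 days (protocol 6.1). Time on OTX-101 totals 52 weeks in both cohorts (synopsis), i.e. 52 × 7 = 364 days. Baselines are as in SAP 7.

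**The plan's own figures.** The schedule gives days since Visit 5a as Day minus 84: 182 − 84 = 98, 273 − 84 = 189 and 364 − 84 = 280, all as printed. The durations also agree: (364 − 84)/7 = 40 weeks and (448 − 84)/7 = 52 weeks.

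**Time on drug at each scheduled examination.** For OTX-101-origin subjects it equals the study Day. For vehicle-origin subjects it is the study Day minus 84.

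| Cohort and rule | Days on drug at tabulated visits | First value as share of 364 days | Longest stretch without a scheduled value |
|---|---|---|---|
| OTX-101-origin, SAP rule | 182, 273, 364 | 182/364 = 50.0% | 182 days |
| OTX-101-origin, Visit 5 added | 84, 182, 273, 364 | 84/364 = 23.1% | 182 − 84 = 98 days |
| Vehicle-origin, SAP rule | 98, 189, 280, 364 | 98/364 = 26.9% | 98 days |

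**Effect of the Visit 6 window.** For OTX-101-origin subjects, 175/364 = 48.1% to 189/364 = 51.9%. For vehicle-origin subjects, (175 − 84)/364 = 25.0% to (189 − 84)/364 = 28.8%.

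**What the rule removes and what the schedule never collects.** No examination is scheduled between Day 84 and Day 182. Of the 182 days before the first tabulated on-drug value, the last 98 would be empty under any display rule. The rule accounts only for Study 001 visits up to Day 84.

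**Which variables exist at Day 84.** VA is explicit, through the entry criterion. IOP is an inference: Visit 5 assessments are not repeated at Visit 5a, Visit 5a collects no IOP, and the vehicle-origin baseline needs an IOP from before the first OTX-101 dose. That value could come from an earlier Study 001 visit, and the Study 001 schedule is not among the documents.

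**The case against.** The best defence is that an extension report may reasonably confine itself to extension visits plus baseline. No hypothesis is tested, and the cohorts differ in display because Visit 5 is on-drug for one and pre-drug for the other. Protocol 11.8 promises a merged dataset, not by-visit VA and IOP rows. Its one specific display instruction concerns adverse events, and protocol 11.5.1.1 speaks only of certain analyses. Study 001 data are used in these tables, as baseline.

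Much of this is fair. The protocol does not prescribe the rows. But the merge is set out under Safety Analyses, VA and IOP are named safety assessments in protocol 9.4, and its stated purpose is to cover a year of exposure. Tables that omit every on-drug Study 001 value do not carry that out for these variables, and SAP 8 should say so if it is intended.

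Several stronger readings are tempting, and the documents do not support them:

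- *Half a year of results is hidden.* The gap from Day 84 to Day 182 belongs to the visit schedule. The only hidden visit the documents identify is Visit 5.
- *There can be no on-drug result in the first half of the year.* A Visit 6 held on Days 175 to 181, or an early-discontinuation visit (protocol 10.5 includes VA and IOP), could supply one. The statement holds for nominal scheduled visits.
- *Early changes are invisible.* Day 182 is reported as change from Day 0, so anything that persists still shows. A Day 84 row adds only changes present at that visit.
- *The Study 001 report cannot fill the gap.* That report is not available here. Its randomised arm includes these subjects as well as those who left early, so for safety in the first 12 weeks it may be the less selected source.
- *The data are lost.* They remain in Study 001, and the SAP does not say whether the extension listings include them.

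**Conclusion.** The point holds at modest size. For the OTX-101-origin cohort, the VA table, and probably the IOP table, contains no scheduled on-drug value before Day 182, 50% of the planned year (48.1% to 51.9% across the visit window), although VA was measured on drug at Day 84. This does not carry out the one-year merge in protocol 11.8, and SAP 8 does not declare it. What is lost is at least one on-drug VA row: the chance to see in these tables a change present at Day 84 but gone by Day 182.

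The conclusion assumes nominal visit days and ignores the entry gap of up to 14 days after Visit 5. It reads the merge in protocol 11.8 as intended to feed the safety tables. The IOP half also assumes that IOP was measured at Visit 5 or at another Study 001 visit after the first dose.

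**What to change.** In SAP 7.7 and 7.8, replace the display sentence with wording such as: *Results will be presented for the appropriate baseline visit and all extension visits and, for subjects randomised to OTX-101 0.09% in Study 001, for all Study 001 visits after the first dose of OTX-101 0.09% at which the variable was measured (at least Visit 5, Day 84).* Show these rows with change from baseline in Tables 14.3.4 and 14.3.5, and state that Listings 16.2.8.1 and 16.2.8.2 include them. Vehicle-origin subjects need no new rows, since their Study 001 treatment was vehicle.

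The cost is SAP wording and one or more rows in two tables. The data are already collected, and the Study 001 data are already needed for baseline. The new rows need a footnote saying that they cover only subjects who completed Study 001 and enrolled in the extension, and that Day 84 VA is truncated because entry required better than 20/200 in both eyes at that visit.

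If the sponsor prefers to keep the restriction, SAP 8 should declare it as a change from protocol 11.8 and give the reason. SAP 7.10 limits slit lamp results to extension visits as well; the documents do not show what was examined by slit lamp in Study 001, so the sponsor should check whether the same decision applies there.

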### **7.9. Ophthalmoscopy/Dilated Fundoscopy**

The observations of ocular ophthalmoscopy and dilated fundoscopy will be summarized in frequency tables based on the ordinal or categorical scales for each measure for each eye by time point and cohort. Only the results from visits during the extension will be presented. A subject data listing will be provided.

### **7.10. Slit Lamp Examination**

The observations of slit lamp examination will be summarized in frequency tables based on the ordinal or categorical scales for each measure for each eye by time point and cohort. Only the results from visits during the extension will be presented. A subject data listing will be provided.

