9.4. Safety Assessments

Safety will be assessed at each visit by corrected Snellen VA, slit lamp examination, IOP, AE documentation, and concomitant medication review. Ophthalmoscopy/dilated fundus examination will be performed at the subject's last visit; i.e., Visit 8 (Day 364) or Visit 9 (Day 448).

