10.5. Early Discontinuation Visit

If the subject is discontinuing the study early, procedures performed will include the following:

- Collect and document all used and unopened study medication materials, if available; otherwise arrange for the subject to return them
- AE assessment
- Concomitant medication review
- Urine pregnancy test (women of childbearing potential only)
- Corrected Snellen VA
- Slit lamp examination
- IOP
- Ophthalmoscopy/dilated fundus examination

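### SAP 7.9 and 7.10 tabulate slit-lamp and fundus findings without any pre-OTX-101 baseline or shift, so the tables show on-drug prevalence and not new or worsened findings

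*SAP*

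**What the plan says.** Protocol 9.4 puts the slit lamp on the same footing as visual acuity and IOP: "Safety will be assessed at each visit by corrected Snellen VA, slit lamp examination, IOP, AE documentation, and concomitant medication review". The same section places the dilated fundus examination at the subject's last visit.

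The SAP then reports these examinations in two ways.

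- **Visual acuity and IOP.** SAP 7.7 calls for "Descriptive statistics of the observed and change from baseline Snellen VA expressed as equivalent logMAR", by eye, visit and cohort, and SAP 7.8 does the same for IOP. Both sections say "Only the results from visits during the extension plus the appropriate baseline visit will be presented".
- **Slit lamp and fundus.** SAP 7.10 and 7.9 call for frequency tables by eye, time point and cohort. Each ends with "Only the results from visits during the extension will be presented".

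SAP 10 lists one by-eye table for each examination (14.3.6 slit lamp, 14.3.7 fundus) and no shift table. The baseline definition in SAP 7 is general, "Baseline measurements will be the last measurement for the corresponding variable prior to the first dose of OTX-101 0.09"%, but neither 7.9 nor 7.10 uses it.

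At entry to the extension, Protocol 10.1 states: "Assessments conducted at Visit 5 of Study OTX-101-2016-001 are not repeated". The schedule of procedures marks no visual acuity, slit-lamp, IOP or fundus examination at Visit 5a. On the parent study's data, Protocol 11.8 says that "the safety data recorded during Study OTX-101-2016-001 will be merged to produce a dataset encompassing one year of exposure to treatment".

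**The concern.** Long-term safety is the only objective, and the drug is applied to the eye. A reader of the slit-lamp and fundus tables will want to know how many eyes developed an abnormality, or got worse, after OTX-101 was started. A table of on-drug frequencies cannot answer that, because an abnormality seen at Visit 6 may have been there before the first dose.

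Pre-existing findings are plausible in this population. The disease itself affects the ocular surface. The exclusion criteria remove several conditions, including pterygium, conjunctivochalasis, chronic uveitis, a history of herpes keratitis, active eye disease needing medication and severe ocular conditions. They do not remove everything: stable macular disease is allowed, and no lens exclusion is named although the lens is one of the slit-lamp structures.

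**Working it through.** **1. Could any extension examination serve as a pre-drug baseline?** The inputs are the nominal study days in the schedule of procedures: Visit 5a Day 84, Visit 6 Day 182, Visit 7 Day 273, Visit 8 Day 364, Visit 9 Day 448. The first OTX-101 dose is at Day 0 for subjects randomised to OTX-101 in the parent study and at Visit 5a (Day 84) for those randomised to vehicle.

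Nominal days on OTX-101 = study day − day of first OTX-101 dose.

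| Slit-lamp examination | From vehicle | From OTX-101 |
|---|---|---|
| Visit 6 | 182 − 84 = 98 | 182 − 0 = 182 |
| Visit 7 | 273 − 84 = 189 | 273 |
| Visit 8 | 364 − 84 = 280 | 364 |
| Visit 9 (if continuing) | 448 − 84 = 364 | not applicable |

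The vehicle column reproduces the schedule's own row of days since Visit 5a (98, 189 and 280 for Visits 6, 7 and 8). The text of Protocol 10.2.1 prints Day 128 for Visit 6, against 182 in its heading and in the schedule. I used 182; either day falls after the first dose.

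The fundus has one scheduled examination per subject, at the final visit: nominally 364 days on drug, or 280 for a subject from vehicle who ends at Visit 8. Protocol 10.5 adds slit-lamp and fundus examinations at early discontinuation. These may come sooner, but in a safety population defined by at least one dose they also follow the start of drug. So no scheduled extension examination precedes the first dose.

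**2. Pre-drug time points tabulated.** Visual acuity 1, IOP 1, slit lamp 0, fundus 0.

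**3. What the planned tables can identify.** For one examination and one eye, let N be the subjects examined, A the number abnormal at the visit and B the number abnormal before drug. The number newly abnormal lies between max(0, A − B) and min(A, N − B). With B not shown, the range is 0 to A.

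Take N = 258, the number enrolled and exposed in SAP 9, pooling cohorts for simplicity. The prevalences are assumptions for illustration only, as the documents give none.

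| Assumed prevalence at the visit | A | Newly abnormal, B unknown |
|---|---|---|
| 5% | 13 | 0 to 13 |
| 10% | 26 | 0 to 26 |
| 20% | 52 | 0 to 52 |
| 40% | 103 | 0 to 103 |

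**4. Would a baseline column be enough?** Not always. With A = 52 and B = 13, the range narrows to 52 − 13 = 39 up to min(52, 245) = 52. With A = B = 52 it is still 0 to min(52, 206) = 52, because new and resolved findings can cancel. A within-eye shift table gives the count exactly among eyes with both examinations.

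**The case against.** The best defence is that the plan already separates new from old where it matters most. The synopsis names ocular and non-ocular AEs as the criterion for evaluation. Under SAP 3.5.1 an abnormal result becomes an AE if it causes signs or symptoms, is clinically significant, or needs added or changed therapy. A condition present before consent counts only if it worsens. The treatment-emergent AE tables then report these events by system organ class, preferred term, intensity and relationship. This stands, and it confines the gap mainly to abnormalities that do not meet those conditions.

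It can also be said that change from baseline suits continuous measures and that the different wording for categorical examinations may be deliberate. That may be so, but SAP 7 already defines a baseline that could be applied to categories. The by-visit slit-lamp tables can show a trend in prevalence from Visit 6 onward, though not change from before drug or change within an eye. Listings 16.2.8.3 and 16.2.8.4 are planned, but the SAP does not say that they include pre-drug examinations.

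The most serious limit is that neither document sets out the parent study's slit-lamp or fundus schedule. Protocol 10.1 and 11.8 only imply earlier examinations. A reader might infer that the SAP discards baseline data it holds. The documents do not establish that, least of all for the fundus. Nor does Protocol 11.8 promise a shift table; it promises a merged dataset.

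**Conclusion.** The point holds as a cheap improvement. As specified, Tables 14.3.6 and 14.3.7 show prevalence after the start of OTX-101 and cannot show new onset or worsening. This follows from the SAP wording and the visit schedule alone, and it is true whether or not the parent study holds a pre-dose examination. That question decides only whether the gap can be filled or must be disclosed.

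The size of the effect cannot be estimated; the ranges above show what the tables leave open, not what is expected. A reader might go further and infer that new ocular harm would go unreported, or that the study's safety conclusion is unsound. The documents do not support either, because clinically relevant abnormalities are captured as AEs and AEs are the stated criterion.

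**What to change.** - **SAP 7.10.** Present the extension visits together with the baseline visit, as SAP 7.8 does for IOP, using the SAP 7 definition. Add one per-eye shift table by cohort, from baseline to the final or early-discontinuation visit, among eyes with both examinations. Show the number of eyes lacking either one, since SAP 6 imputes nothing.
- **SAP 7.9.** Do the same if the parent study recorded a fundus examination before the first OTX-101 dose.
- **Either examination, if the parent study has none before that dose.** State that new-onset findings cannot be identified from the examination data.
- **SAP 10.** Add the shift table or tables after 14.3.6 and, where applicable, 14.3.7.

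The cost is SAP wording and one or two descriptive tables drawing on parent-study data, with no new visits or procedures. Those data are already needed: with no eye examination at Visit 5a, the visual acuity and IOP baselines must come from the parent study. The gain is also limited, because a shift in a single-arm study shows timing and not cause.

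Protocol 11.2 and SAP 7 define baseline differently for subjects who came from vehicle. That should be reconciled as a separate point before the shift tables are programmed.
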